## 1 LIST OF ABBREVIATIONS AND DEFINITIONS

AE	Adverse Event
AKIN	Acute Kidney Injury Network
ARC	Academic Research Consortium
BARC	Bleeding Academic Research Consortium
CABG	Coronary artery bypass graft
CAD	Coronary Artery Disease
CCS	Canadian Cardiovascular Society
CI	Chief Investigator - The overall lead researcher for a research project (Outside the UK the term Coordinating Investigator or Investigator may be used). Chief investigators are responsible for the overall conduct of a research project.
CMD	Coronary Microvascular Dysfunction
CNS	Central Nervous System
CFR	Coronary Flow Reserve
CT	Computed Tomography Scan
CTCA	Computed Tomography Coronary Angiogram
CT-FFR	Computed Tomography Fractional Flow Reserve
CTU	Clinical Trials Unit
Datix	Incident reporting and risk management platform
DMC	Data Monitoring Committee
ECG	Electrocardiogram
eCRF	Electronic Case Report Form
EDI	Equity, Diversity and Inclusion
FFR	Fractional Flow Reserve
GSTFT	Guys and St Thomas' NHS Foundation Trust
HFpEF	Heart Failure with preserved Ejection Fraction
HFReF	Heart Failure with reduced Ejection Fraction
HRA	Health Research Authority
ICHOM	International Consortium for Health Outcomes Measurement
KCCQ-OSS	Kansas City Cardiomyopathy Questionnaire Overall Summary Score
KCL	King's College London
LVEF	Left Ventricular Ejection Fraction
MCID	Minimum Clinically Important Difference
MI	Myocardial Infarction
NHPR	Non-hyperaemic pressure ratio
NHS	National Health Service
NICE	National Institute for Health and Care Excellence
NIHR	National Institute for Health and Care Research
NT-pro-BNP	N-terminal pro B-type natriuretic peptide
NYHA	New York Heart Association
OAC	Oral anticoagulant
ORBITA	Objective Randomised Blinded Investigation with Optimal Medical Therapy or Angioplasty in Stable Angina ( Randomised Trial )
PAC	Patient Advisory Committee
Participant	An individual who takes part in a clinical trial
PCI	Percutaneous Coronary Intervention

PI	Principal Investigator - An individual responsible for the conduct of the research at a research site. There should be one PI for each research site. In the case of a single-site study, the chief investigator and the PI will normally be the same person.
PIC	Participant Identification Centre
PPI	Patient and Public Involvement
PROMS	Patient Reported Outcome Measures
R&D	Research & Development
REC	Research Ethics Committee
SAE	Serious Adverse Event
SGLT2i	Sodium glucose cotransporter-2 inhibitor
SOP	Standard Operating Procedure
Sponsor	The organisation or partnership that takes on overall responsibility for proportionate, effective arrangements being in place to set up, run and report a research project.
SWAT	Study Within A Trial
TIA	Transient Ischemic Attack
TIMI	Thrombolysis In Myocardial Infarction
TMG	Trial Management Group
TSC	Trial Steering Committee
VARC	Valve Academic Research Consortium
VFR	Volumetric Flow Reserve
WPD	Working Practice Document

## 2 SUMMARY/SYNOPSIS

Title	REvascularisation for heart failure with PReserved ejection fraction and Ischaemia: EValuation of Efficacy and mechanistic Description (REPRIEVED)
Protocol Short Title/Acronym	Coronary artery stents in heart failure with preserved ejection fraction: The REPRIEVED Trial
Study Phase if not mentioned in title	Phase II
Is the study a Pilot?	No
IRAS Number	330189
REC Reference	25/LO/0277 (London - Riverside REC)
EDGE reference	174792
Study Duration	Five years
Methodology	Prospective, multi-centre, randomised, double-blind, placebo procedure-controlled trial
Health condition(s) or problem(s) studied	Heart failure with preserved ejection fraction (HFpEF) and coronary artery disease
Purpose of clinical trial	To improve the quality of life of patients with HFpEF and coronary artery disease
Primary objective	To establish the efficacy of percutaneous coronary intervention at improving quality of life for patients with HFpEF and coronary artery disease
Secondary objective (s)	To examine the mechanistic link between ischaemia and quality of life in this population, and how this is modified by percutaneous coronary intervention
End of study definition	All study data collected and final database locked
Number of Participants	350
Study Type	Randomised controlled trial
Human Tissue Samples (if applicable)	Research bloods: 5ml blood for full blood count, 5ml for renal function, troponin and NT-pro BNP (only if not taken as part of standard of care at participating sites).
Data collected/storage (if applicable)	Data collection and processing at the London School of Hygiene & Tropical Medicine Clinical Trials Unit using an electronic data capture system hosted by Sealed Envelope Ltd.  Subsequent transfer of final datasets (identifiable and pseudonymised) to King's College London for long term storage and secondary analysis.

### 3 INTRODUCTION

#### *Heart failure with preserved ejection fraction*

Heart failure with preserved ejection fraction (HFpEF) is a debilitating condition that accounts for over half of new diagnoses of heart failure, is increasing in prevalence and is associated with increased cardiovascular mortality compared to matched controls without HFpEF. The primary symptoms are breathlessness, fatigue, peripheral oedema and effort intolerance. The condition is characterised by impairment of cardiac function due to structural cardiac abnormalities despite a normal left ventricular ejection fraction (LVEF) at rest. Development of HFpEF is often associated with hypertension, diabetes, obesity and chronic kidney disease, particularly where these occur together and with increasing age. It is estimated that 400,000 people in the UK have HFpEF, accounting for 2.5% of emergency hospital admissions and a significant proportion of the £2 billion per year that the NHS spends on heart failure treatment.

Widespread recognition of the condition has only been achieved in the last decade. The prevalence of HFpEF is higher in women and minoritised ethnic populations, who have been under-served by interventional heart failure research. Consequently, treatment remains under-developed and evidence-based treatment for HFpEF remains limited to only two repurposed antidiabetic drugs (sodium glucose cotransporter-2 inhibitors (SGLT2i) and semaglutide. SGLT2i are the only drug class to also reduce mortality, whilst semaglutide was tested only in patients with an obesity-HFpEF phenotype. Current European guidelines recommend patients with HFpEF receive diuretics, SGLT2i and optimal treatment of comorbidities. This contrasts sharply with heart failure with reduced ejection fraction (HFrEF), where evidence-based developments in drugs, devices and interventions have reduced mortality substantially over the past four decades.

#### *Coronary artery disease in HFpEF*

Coronary artery disease is an important contributor to the development of HFpEF. Observational and epidemiological studies have consistently shown a prevalence of coronary artery disease in HFpEF of 35-65%. Epidemiological studies have found clear associations between prevalent coronary artery disease and incident HFpEF.

The mechanistic link between coronary artery disease and the development of HFpEF is hypothesised to be inducible myocardial ischaemia. Inducible ischaemia (inadequate capacity to augment blood flow to meet the metabolic demands of the myocardium) may arise due to stenoses of the epicardial coronary arteries (epicardial coronary artery disease) or abnormalities of the arteriolar circulation (coronary microvascular dysfunction (CMD)), though the effects on the myocardium are expected to be similar. The role of ischaemia in the pathogenesis of HFpEF is well recognised, though greater research focus has been given to CMD than epicardial coronary artery disease.

Studies in patients with HFpEF and CMD have demonstrated higher left ventricular work, oxygen demand and myocardial blood flow at rest but blunted rises in these indices during stress compared with controls. This inadequate rise in supply relative to demand impairs left ventricular systolic and diastolic function during exertion, limiting cardiac reserve and resulting in detectable myocardial injury via troponin release after exercise. This impairment of diastolic function also worsens ischaemia (as myocardial perfusion is dependent on diastolic ventricular relaxation) resulting in a deleterious cycle of ischaemia and impaired ventricular performance. Patients may experience these effects as angina, breathlessness, effort intolerance or fatigue, often with significant overlap, and whether breathlessness represents an angina equivalent in patients with heart failure remains an important unanswered question.

In addition to the acute effects of ischaemia on symptoms and functional capacity in HFpEF, it is recognised that recurrent episodes of ischaemia result in chronic injury and myocardial fibrosis (which leads to persistent worsening of diastolic function). Longitudinal studies have shown larger deteriorations in LVEF over time in individuals with HFpEF and coronary artery disease, compared to those with HFpEF alone. Developing the evidence base relating ischaemia from epicardial coronary artery disease to symptoms, fibrosis and longitudinal changes in left ventricular function in HFpEF would therefore complement ongoing parallel work relating to CMD.

### ***Percutaneous coronary intervention***

Percutaneous coronary intervention (PCI), also referred to as coronary angioplasty and stenting, is an established treatment for coronary artery disease when the patient presents with limiting angina despite optimal pharmacological therapy or an acute myocardial infarction. Coronary patency is restored by balloon dilatation of significant coronary stenoses, followed by placement of a stent which enhances patency in the long term. The procedure is minimally invasive and associated with an in-hospital mortality of 0.14% and risk of myocardial infarction or stroke of 0.3%. The cost of elective PCI in the NHS is modest compared to many other interventions (with an average tariff cost of £1782 for an elective procedure in 2019/20). Despite the causal association and mechanistic link between coronary artery disease and HFpEF, no randomised study has assessed the efficacy or mechanistic benefits of PCI in this population.

PCI is an attractive option to improve quality of life in patients with HFpEF and coronary artery disease. Treatment with PCI has been shown to improve myocardial perfusion and attenuate the development of systolic and diastolic dysfunction during exertion. Long-term improvement in the ischaemic substrate may also reduce the development of myocardial fibrosis and progression to left ventricular systolic dysfunction which has been recognised in this population over longitudinal follow-up. Furthermore, there are concerns that many first-line drugs traditionally used to treat ischaemia may worsen symptoms in patients with HFpEF. The use of beta blockers in HFpEF is associated with chronotropic incompetence, impaired exercise capacity and higher levels of natriuretic peptide, whilst chronic use of nitrates is associated with worsening endothelial function and reduced exercise capacity in this population. A treatment which avoids these drug side effects whilst ameliorating ischaemia may therefore be beneficial. Factors which might attenuate the benefit of PCI include the high prevalence of coronary microvascular dysfunction in HFpEF which may leave a (lessened) ischaemic substrate after treatment and the extent of pre-existing cardiac remodelling which may not be reversible, as well as the systemic nature of the condition.

Despite these observational associations and mechanistic explanations for a potential benefit to PCI in HFpEF and coronary disease, the question remains unstudied. The ClinicalTrials.gov and ISRCTN registries report no trials of coronary revascularisation amongst 104 interventional HFpEF studies which are either recruiting or in set-up, though multiple studies are investigating the use of pharmacological treatment to mitigate ischaemia due to CMD or epicardial coronary artery disease in this population. National Institute for Health and Care Excellence (NICE) and international cardiology guidelines on the management of heart failure make no recommendations for the management of coronary artery disease in patients with HFpEF, contrasting with heart failure with reduced ejection fraction (HFrEF) where multiple recommendations are made based on high-quality randomised data. Exploring the mechanistic links between ischaemia and symptoms in HFpEF and the efficacy of modifying them with coronary revascularisation is therefore a pressing and important question well suited to a phase-2 randomised trial.

## 4 TRIAL OBJECTIVES AND PURPOSE

### Aims:

1. To establish the efficacy of PCI at improving quality of life for patients with HFpEF and coronary artery disease.
2. To examine the mechanistic link between ischaemia, quality of life and the change in these measures after PCI in this population.

### Hypotheses:

#### *Efficacy*

In patients with HFpEF and coronary artery disease, treatment with PCI is associated with superior quality of life, measured with the KCCQ-OSS, compared to a placebo procedure.

#### *Mechanistic*

In patients with HFpEF and coronary artery disease:

- The severity of symptoms correlates with the extent of myocardial ischaemia measured by coronary flow reserve (CFR).
- Treatment of epicardial coronary disease by PCI will improve CFR.
- The change in quality of life following PCI correlates with pre-randomisation CFR and the change in CFR following PCI.

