#### Outcome measures:

- **Primary efficacy:** The primary efficacy outcome is the difference in KCCQ-OSS between treatment groups at 6-month follow-up. The Kansas City Cardiomyopathy Questionnaire (KCCQ) is the most widely used disease-specific tool for patient reported quality of life outcomes in heart failure, has been specifically validated in HFpEF and is the recommended tool for assessing functional and psychosocial outcomes in the International Consortium for Health Outcomes Measurement (ICHOM) standard outcome set for heart failure published in 2020.
- **Primary mechanistic:** The primary mechanistic outcome is the difference in CFR between treatment groups, after PCI has been performed in the PCI group. CFR is an independent predictor of future adverse cardiovascular events and allows us to determine the relationship between the severity of epicardial and microvascular disease and quality of life.
- **Secondary outcomes:** Key secondary outcomes include all-cause death and hospitalisation for heart failure. Further secondary outcomes include the efficacy of blinding (assessed using standard tools), the ICHOM standard outcome set for heart failure, individual components of the KCCQ (including total symptom score and clinical summary score), New York Heart Association (NYHA) functional class, difference in NT-pro-BNP at six months and difference in left ventricular ejection fraction (LVEF) and diastolic function (mitral E/e') at six months.
- **Secondary mechanistic:** Secondary mechanistic outcomes include change in invasively measured FFR, CFR and microvascular resistance from pre- to post-PCI in all target coronary arteries measured during the PCI procedure.

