### **6.5.2 On the day of the intervention**

On the day of the trial intervention, ongoing consent for the study will be confirmed and clinical consent for the invasive procedure obtained by the unblinded PI. Procedures will be performed by either the unblinded PI or an unblinded sub-investigator. Participants will receive pre-treatment with antiplatelet medication (aspirin 300mg and clopidogrel 300-600mg per local protocol). The KCCQ will be repeated to measure early changes in quality of life with medical optimisation.

Coronary angiography will be performed using standard procedure, preferentially via radial access. Following coronary angiography, a detailed physiological assessment will be performed in all target coronary arteries, including measures of fractional flow reserve (FFR), coronary flow reserve (CFR) and microvascular function. Left ventricular end diastolic pressure will be measured at rest and during handgrip exercise.

Before randomisation, patients will receive headphones playing music to ensure auditory isolation, and patients will be sedated using incremental doses of benzodiazepines and opiates to a deep level of conscious sedation.

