## 16 STATISTICAL CONSIDERATIONS

A detailed statistical analysis plan will be written and signed off prior to database lock and unblinding of trial data. For the KCCQ-OSS and CFR measures, differences in mean levels of the outcome measures between treatment groups at the relevant timepoints will be calculated, together with 95% confidence intervals, using a linear mixed model with treatment group, categorical treatment by timepoint interaction and baseline outcome measures included in the model (random intercept, unstructured correlation). It may be necessary to examine the measures for transformations to adhere to the assumptions of the linear mixed model or use bootstrapping techniques if a suitable

transformation cannot be found. For the primary analysis, any patient who dies will be excluded but as a sensitivity analysis a value of 0 will be imputed. All analyses will be on an intention-to-treat basis. Key secondary outcomes include all-cause death and/or hospitalisation for heart failure which will be assessed and compared between groups with hazard ratios using a Cox proportional hazards model. In addition risk differences will also be presented together with 95% confidence intervals at 6 months. The individual components of all-cause-death and hospitalisation for heart failure will also be analysed. In addition, groups will be compared using the unpaired win ratio method with a prespecified hierarchy of all-cause death, hospitalisation for heart failure and difference in KCCQ-OSS  $\geq 7$  between participants at six months. Sensitivity analyses will be reported excluding any participants who underwent emergency unblinding. Whilst the sample size will not permit definitive analyses based upon subgroups, hypothesis generating subgroup analyses will be performed to assess for differential treatment response based on age, sex and baseline NT-pro-BNP.

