### **16.1 Sample size calculations**

In pilot data from our REVIVED-BCIS2 trial (which has been selected as calculations can be performed using individual participant data and represents the only randomised comparison of PCI to medical treatment in a heart failure population), the baseline KCCQ-OSS was 60.9 with a between-group difference at six months of 6.5 (95% confidence interval 3.5 to 9.5) points. There was a high degree of correlation between baseline and six-month scores (correlation coefficient: 0.67). Though the standard distributions of scores at each timepoint were non-normally and widely distributed, the distribution of change in score from baseline to follow-up was close to normally distributed. Assuming similar baseline values, a standard deviation of KCCQ-OSS of 25, correlation coefficient of 0.6 and an alpha of 0.05, a total of 350 participants are required to have in excess of 85% power to detect a minimum clinically important difference (MCID) of 7 points, allowing for 10% withdrawals or losses to follow-up. If correlation were higher (0.65) a sample size of 350 participants will achieve in excess of 90% power for a difference of 7. If the standard deviation were increased (27), we would retain in excess of 80% power for a MCID of 7. The inclusion of a three month follow-up timepoint will enable repeated measures of KCCQ-OSS which will further increase power. A review of the sample size assumptions blinded to treatment allocation will be made after 1 year of recruitment to assess the correlation between baseline and follow up measures; consideration will be given to extending the sample size at this point if recruitment permits.

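### The third mechanistic hypothesis links quality-of-life change after PCI to baseline CFR with no placebo comparison, so as worded it cannot separate benefit from PCI from change that would have happened anyway

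*Protocol*

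**What the plan says.** Section 4 (Mechanistic hypotheses) states: "The change in quality of life following PCI correlates with pre-randomisation CFR and the change in CFR following PCI". The efficacy hypothesis just above it names the placebo procedure as comparator; this one does not. The first mechanistic hypothesis posits that symptom severity is related to CFR. The secondary objective in the synopsis asks how the link between ischaemia and quality of life is modified by PCI.

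Section 6.5.2 describes a physiological assessment, "including measures of fractional flow reserve (FFR), coronary flow reserve (CFR) and microvascular function", before its paragraph on preparing the patient for randomisation, and does not restrict it to one arm. The schedule in Section 6.12 collects the KCCQ at baseline, at the procedure visit and at 3 and 6 months. Change in CFR appears in Section 5.1 as part of a secondary outcome: "change in invasively measured FFR, CFR and microvascular resistance from pre- to post-PCI in all target coronary arteries".

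Section 16 analyses KCCQ-OSS and CFR "using a linear mixed model with treatment group, categorical treatment by timepoint interaction and baseline outcome measures included in the model". It adds hypothesis-generating work: "subgroup analyses will be performed to assess for differential treatment response based on age, sex and baseline NT-pro-BNP". CFR is not in that list, and no test is given for the third mechanistic hypothesis.

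**The concern.** Whether PCI helps more when CFR is low is a question about the difference between arms. A correlation among PCI recipients mixes two things: CFR as a predictor of benefit from PCI, and CFR as a marker of participants whose KCCQ would move anyway, through natural course, optimised medical therapy or placebo response.

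The protocol's own premises make the second possibility live. If low CFR goes with low baseline KCCQ, and that link weakens over six months, low-CFR participants will show larger average gains in either arm. A PCI-only analysis would then resemble the pattern expected if ischaemia drove the benefit. The placebo arm is there to remove this ambiguity, and the hypothesis as worded does not use it. At stake is one stated aim and the planned mechanistic paper.

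**Working it through.** **Inputs.** From Sections 16.1 and 6.4.1: "a standard deviation of KCCQ-OSS of 25, correlation coefficient of 0.6 and an alpha of 0.05", 350 participants allocated 1:1, 10% loss and a 7-point difference. Evaluable per arm: 175 × 0.9 = 157.5. A two-sided test is assumed. The correlations of CFR with baseline KCCQ (r0) and with 6-month KCCQ (r1) are not in the protocol, so a range is shown.

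**1. The plan's own power figure.** Baseline-adjusted SD = 25 × √(1 − 0.6²) = 20. Standard error = 20 × √(2/157.5) = 2.254. 7/2.254 = 3.106, so power = Φ(3.106 − 1.960) = 87.4%, against a stated figure of more than 85%. The other two cases also reproduce: 90.5% at correlation 0.65 (stated above 90%) and 82.0% at SD 27 (stated above 80%). No figure is stated for the CFR hypothesis.

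**2. Correlation of CFR with KCCQ change within one arm.** With equal SDs at both times and no effect modification,

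corr(CFR, change) = (r1 − r0) / √(2(1 − 0.6)) = (r1 − r0) / 0.894.

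If CFR relates to 6-month KCCQ only through baseline KCCQ, then r1 = 0.6 × r0. For r0 = 0.3 this gives (0.18 − 0.30)/0.894 = −0.134. By Fisher's z with n = 157, atanh(0.134) × √154 = 1.675, and the rejection rate is about 38.8%. The same formula gives about 20% at r0 = 0.2 and 61% at r0 = 0.4. The negative sign means that lower CFR goes with larger gain.

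**3. Baseline-adjusted regression within one arm.** The standardised CFR coefficient is (r1 − 0.6 × r0)/(1 − r0²). It is zero when r1 = 0.6 × r0. When r1 = r0 = 0.3 it is 0.12/0.91 = 0.132, which is not zero and has the opposite sign.

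**4. Simulated rejection rates.** 157 per arm, constant 7-point PCI effect, no effect modification, 3,000 runs per row:

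| r1 | r0 | One-arm, change score | One-arm, baseline-adjusted | Treatment-by-CFR interaction, both arms |
|---|---|---|---|---|
| 0.6 × r0 (only through baseline) | 0.2 | 19% | 5% | 5% |
| | 0.3 | 39% | 5% | 5% |
| | 0.4 | 61% | 4% | 4% |
| 0.8 × r0 (half that attenuation) | 0.2 | 9% | 9% | 5% |
| | 0.3 | 13% | 15% | 5% |
| | 0.4 | 19% | 29% | 5% |
| r0 (none) | 0.2 | 6% | 24% | 5% |
| | 0.3 | 5% | 51% | 5% |
| | 0.4 | 5% | 78% | 5% |

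Neither one-arm analysis holds its level throughout; the interaction does.

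**5. Power of the interaction** (r0 = 0.3, r1 = 0.18): about 19%, 58%, 86% and 99% for a modification of 2.5, 5, 7 and 10 KCCQ points per SD of CFR.

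**The case against.** Section 4 states scientific hypotheses. It names no estimator, test or analysis set, and Section 16 defers detail to an analysis plan that could specify an interaction. That is fair: the protocol does not commit to a one-arm test. What stands is that the wording itself has no comparator, and that the effect modifiers Section 16 does name leave CFR out. An analysis plan that followed both would arrive at the one-arm correlation.

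A reader might infer that regression to the mean makes the correlation misleading as a matter of course. The documents do not support that. KCCQ measurement error unrelated to CFR leaves the change-score correlation unbiased. Inflation in the expected direction needs the CFR–KCCQ link to weaken over time, and the protocol says nothing about that. If untreated ischaemia keeps driving symptoms, the link may persist. Simulated selection of participants with low KCCQ gave 7% to 36% false positives, but in the opposite direction.

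Aim 2 and Objective 2 are also worded as associations, and only the synopsis speaks of modification by PCI. So an associational reading is possible, though it would not answer the synopsis objective. Finally, the placebo arm helps only with baseline CFR: change in CFR is defined from before to after PCI, and no repeat placebo measurement is clearly described.

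**Conclusion.** The point holds as a defect of wording and of the modifier list. As written, the third mechanistic hypothesis cannot distinguish a prognostic role of CFR from a predictive one.

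The size depends on two quantities that the protocol does not give. For r0 between 0.2 and 0.4, the false-positive rate of a one-arm change correlation runs from about 5% (no attenuation) through 9% to 19% (half) to about 20% to 61% (CFR acting only through baseline KCCQ). The top range should not be quoted alone. Where the change correlation is safe, the baseline-adjusted one-arm regression is not (24% to 78%), so choosing between the two does not remove the problem.

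It would go too far to call the mechanistic results uninterpretable or to say that an invalid test is planned. The primary efficacy and primary mechanistic outcomes are between-group comparisons and are untouched, and no sample-size claim rests on this hypothesis.

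**What to change.** - **Section 4:** restate the baseline-CFR part as: the effect of PCI versus placebo on 6-month KCCQ-OSS varies with pre-randomisation CFR.
- **Section 16:** test it by a treatment-by-CFR interaction, with CFR continuous, in a model on both arms containing treatment, CFR, their interaction and baseline KCCQ-OSS. Add CFR to the named effect modifiers with the same hypothesis-generating status.
- **Change in CFR:** describe its association with quality-of-life change as within the PCI arm and non-randomised.

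The cost is the wording of one hypothesis and one model term. No new measurement is needed, provided that the pre-randomisation CFR described in Section 6.5.2 is recorded in both arms; the procedure-visit list in Section 6.10.2 does not name CFR and could do so. The downside is limited power: good for a modification of 7 points or more per SD of CFR, only about 58% for 5 points, and poor below that. A non-significant interaction should therefore be reported with its confidence interval and not read as absence of modification.
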